Both the in-person (contact 2) and the remote (contact 3) intervention visits will be conducted by research study staff with diabetes care experience (e.g. registered nurse or RDN). Full details of the SDA intervention components can be found in the SDA manual of procedures (SDA-MOP), which was designed for this study. Use of the manual will help ensure that each participant receives similar messaging and materials.

In brief, the SDA arm participants will receive introduction to the Dexcom G7 and its accompanying phone apps using manufacturer-provided materials and resources. The SDA will encourage participants to use the device and apps in the way they feel most useful to them. The SDA is intended to reflect current CGM initiation practices, which focus on technical use of the CGM and a general review of CGM data.

Materials used to support the SDA include:

- Dexcom G7 manufacturer-provided materials
- Educational materials or instructional resources found on the Dexcom website (<https://www.dexcom.com/en-us>)

CGM Initiation in People with T2D

Phase 1: Post-Intervention Period

The post-intervention period is part of the intervention and is defined as approximately the final 10 days of study participation (approximately Day 40 to Day 50). During this time, the participant is instructed to continue to use the CGM device in accordance with the guidance provided based on randomization arm. The participant will also complete one of the two required ASA24 diet recalls during this time.

Phase 1: Study Completion

Study completion occurs approximately Day 50. At the study completion visit, the participant will complete the final post-intervention assessments, including an HbA1c, remaining dietary assessments, and PRO surveys.

Phase 2: Follow-Up Period

The Phase 2 follow-up is approximately four months and it begins the day after the Phase 1 post-intervention period ends; approximately Day 51 to Day 180. There is no intervention during Phase 2. Participants will manage their diabetes with their usual care team (not the study team), this may include adjustments to medications as needed; however, participants are asked **not** to use CGM during this follow-up period.

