During contact 6 (approximately Day 170), participants will be asked to report any serious changes to health, changes to diabetes-related medications, and diabetes device use during the previous 4 months. Participants will complete additional assessments and study staff will apply a 10-day G7 sensor paired with a physically blinded receiver; the process and devices are the same as baseline.

The participant will receive instructions on how to care for the receiver and will wear the G7 sensor for up to 10 days; however, participants will not be able to see their glucose data during this time. Participants will be instructed to contact the study team if the sensor comes loose or falls off earlier than 7 days or for any other sensor-related concerns. If a participant reports fewer than seven days of sensor wear, the participant will have an option to return to the clinic so that study staff can pair another G7 sensor with the physically blinded receiver.

On approximately Day 180, participants will receive a study reminder to complete a final ASA24 diet recall and to return their physically blinded receiver to the study team (e.g. postal mail or in person).

Detailed Schedule of Activities

The study includes approximately seven contacts between study staff and study participants.

Contact	Key tasks
Contact 1: Baseline assessments Day -11 to Day -1 (plus additional days, if needed, to obtain at least seven days of G7 sensor data)	
• Preliminary eligibility confirmed, consent signed• HbA1c to confirm eligibility^a• Demographic/Diabetes self-care data assessment• Diabetes medication assessment• Height, weight, BP• Study team applies G7 sensor and pairs it with a physically blinded Dexcom receiver• ASA24 and DietID assessments

CGM Initiation in People with T2D

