
Contact 6: Follow-up assessments begin
 
Day 170 (+14 days)
 
Follow-up Assessment
	
 • HbA1c • Diabetes medication assessment • Adverse event assessment • Weight, BP • Complete first follow-up period ASA24 diet recall • PRO surveys (Diabetes distress, diet adherence, efficacy, diabetes self-care) • Study team applies G7 sensor and pairs it with a physically blinded Dexcom receiver • Participant wears G7 sensor paired with a physically blinded Dexcom receiver for up to 10 days* 
*If a participant contacts the clinic to report the sensor has fallen off early/failed in fewer than seven days, the participant will be provided an option to return to clinic to pair another G7 sensor with the physically blinded Dexcom receiver. A

CGM Initiation in People with T2D

	minimum of seven days of sensor data is desired, but not required. Data from more than one G7 sensor may be an option to reach 10 days.
Contact 7: Follow-up assessments end Day 180 (+7 days) (plus additional days, if needed, to obtain at least seven days of G7 sensor data) Follow-up Completion	
• Participant receives reminder from study team on approximately Day 180 to:
○ Return the physically blinded receiver to the clinic (e.g. postage-paid envelope)• Complete second follow-up period ASA24 diet recall

16. Study Device Management

Participants who terminate early or who are withdrawn at any point during Phase 1 or Phase 2 will be asked to return the Dexcom G7 receiver to the clinic, if applicable. Any unused G7 sensors may be returned to the clinic or disposed of properly by participant.

17. Early Termination and Participant Withdrawal

A participant can choose to terminate study participation and exit the study at any time and for any reason. Participants who request early termination will be asked for a reason for their decision. A participant can be withdrawn from the study with or without their consent if deemed necessary based on adverse event(s) or for any other reason deemed appropriate by Investigators, such as non-compliance with study instructions. If a participant chooses early termination or is withdrawn, the Investigators will decide whether the participant may be eligible to complete final assessments.

18. Lost to Follow-Up

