Multiple attempts will be made to contact participants who become lost to follow-up. Investigator discretion will determine whether a participant should be withdrawn if reasonable attempts for contact are unsuccessful.

19. Protocol Deviations

A protocol deviation occurs when the study is not conducted according to this protocol. All deviations will be documented in a study deviation log. Investigators and study staff will not knowingly deviate from this protocol except in the cases of protecting participant safety. The Investigators or delegated study staff will notify the IRB of protocol deviations in accordance with IRB policies and procedures.

20. Assessment of Safety

The following definitions will be used in the assessment of safety.

Adverse Event

CGM Initiation in People with T2D

Adverse Event (AE) is any unfavorable and unintended sign (including an abnormal laboratory finding), symptom or disease temporally associated with the intervention, regardless of whether it is considered related to the intervention.

Serious Adverse Event

Serious Adverse Event (SAE) is any adverse event that

- (1) results in death;
- (2) is life-threatening;
- (3) results in inpatient hospitalization or prolongation of existing hospitalization;
- (4) results in a persistent or significant disability/incapacity;
- (5) results in a congenital anomaly/birth defect; or
- (6) based upon appropriate medical judgment, may jeopardize the participant's health and may require medical or surgical intervention to prevent one of the other outcomes listed in this definition.

Life-threatening means the event places the subject at immediate risk of death from the event as it occurred.

Unanticipated Event

An unanticipated event is defined as an event, experience, or outcome that meets **all three** of the following criteria:

- is unexpected; AND
- is related or possibly related to participation in the research; AND
- suggests that the research places subjects or others at a greater risk of harm (including physical, psychological, economic, or social harm) than was previously known or recognized.

Unexpected means the nature, severity, or frequency of the event is not consistent with either:

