- the known or foreseeable risk of adverse events associated with the procedures involved in the research that are described in the protocol-related documents, such as the IRB-approved research protocol, the ICF, and/or other relevant sources of information, such as product labeling and package inserts
- the expected natural progression of any underlying disease, disorder, or condition for the participant experiencing the adverse event, and/or the participant's predisposing risk factor profile for the adverse event.

Unanticipated Problems Involving Risks to Subjects or Others

Unanticipated Problems Involving Risks to Subjects or Others (UPIRTSO) means:

- any problem or event which in the opinion of the Investigator was unanticipated, serious; AND
- at least possibly related to the research procedures

Possibly related means there is a reasonable possibility that the incident, experience, or outcome may have been caused by the procedures involved in the research.

Severity of events will be defined as:

- **Mild** requires minimal or no treatment and does not interfere with the participant's daily activities.

CGM Initiation in People with T2D

- **Moderate** results in a low level of inconvenience or concern with therapeutic measures. Moderate events may cause some interference with the participant’s functioning.
- **Severe** interrupts a participant’s usual daily activity and may require systemic drug therapy or other treatment.

21. Safety Reporting

AEs and SAEs may be obtained by participant report, EMR notification, or incidental finding throughout the study. Participants will be asked to report changes to health or concerns related to study devices during study visits. AEs and SAEs will be documented in the participant’s EMR; however, only reportable AEs and SAEs will be described in end-of-study reporting.

Reportable AE’s include the following:

- Sensor-related reactions or infections requiring treatment by a medical provider and/or prescription medication
- Severe hypoglycemia defined as requiring assistance of another person due to altered consciousness, and requiring another person to actively administer carbohydrate, glucagon, or other resuscitative actions
- Severe hyperglycemia if the event involves diabetic ketoacidosis (DKA) or hyperosmolar hyperglycemic state (HHS), as defined in detail in Kitabchi et al⁴³ and summarized here:

	DKA			HHS

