	Mild (plasma glucose >250 mg/dl)	Moderate (plasma glucose >250 mg/dl)	Severe (plasma glucose >250 mg/dl)	Plasma glucose >600 mg/dl
Arterial pH	7.25–7.30	7.00 to <7.24	<7.00	>7.30
Serum bicarbonate (mEq/l)	15–18	10 to <15	<10	>18
Urine ketone*	Positive	Positive	Positive	Small
Serum ketone*	Positive	Positive	Positive	Small
Effective serum osmolality†	Variable	Variable	Variable	>320 mOsm/kg
Anion gap‡	>10	>12	>12	Variable
Mental status	Alert	Alert/drowsy	Stupor/coma	Stupor/coma

*Nitroprusside reaction method. †Effective serum osmolality: 2[measured Na⁺ (mEq/l)] + glucose (mg/dl)/18. ‡Anion gap: (Na⁺) – [(Cl⁻ + HCO₃⁻) (mEq/l)]. (Data adapted from ref. 13.)

Table taken from Kitabchi et al⁴³

Only reportable AEs and all SAEs will be recorded within an adverse event log with a description including the nature of the event, the date and time of onset and/or frequency, determination of non-serious versus serious, intensity (mild, moderate, severe), duration of the event, relationship to the intervention, the expectedness of the event, and outcome of the event. All reportable AEs and all SAEs will be reviewed and confirmed by a delegated medical doctor or equivalent. All AEs and SAEs must be resolved or deemed stable by a delegated medical doctor or equivalent before a participant completes or withdraws from the study.

Delegated study staff will report all reportable AEs, SAEs, and UPIRTSOs to the IRB in accordance with IRB policies.

22. Study Suspension or Discontinuation

This study will be suspended or stopped prior to completion if information becomes available during the study that indicates as such, this may include information related to adverse events or the potential for adverse events. The study may also be suspended or stopped prior to completion if recruitment

CGM Initiation in People with T2D

challenges or retention issues will impact the ability to properly analyze defined endpoints or for other reasons determined by the Investigator.

23. Statistical Considerations

Phase 1 Statistical Hypotheses

Primary Endpoint: Change in CGM-derived TIR (% time with glucose 70-180 mg/dL) from baseline to post-intervention.

Hypothesis (alternative): Participants randomized to a nutrition-focused approach (NFA) will show a larger increase in CGM-derived TIR from baseline to post-intervention than participants randomized to a self-directed approach (SDA).

Secondary Endpoint: Difference in total HEI score between groups during the post-intervention period.

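### No scheduled adverse event enquiry follows the final 10-day blinded sensor wear, and the AE definition leaves its coverage of baseline and Phase 2 device wear unclear

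*Combined protocol and SAP*

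**What the plan says.** **Contact 6 (about Day 170).** The task list in section 15, Detailed Schedule of Activities, includes "Adverse event assessment" and, later in the same list, "Study team applies G7 sensor and pairs it with a physically blinded Dexcom receiver". Section 15, Phase 2: Follow-Up Period, describes the enquiry at this visit: participants report serious health changes, "changes to diabetes-related medications, and diabetes device use during the previous 4 months".

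**Contact 7 (about Day 180).** The entry opens "Participant receives reminder from study team on approximately Day 180 to" and goes on to the return of the blinded receiver, for example by post, and the second follow-up diet recall. No adverse event item is listed. Section 4 gives the visit type as N/A, and the notes to section 3 identify this as the last follow-up contact.

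**Section 21, Safety Reporting.** "Participants will be asked to report changes to health or concerns related to study devices during study visits". The section also accepts events from participants, the electronic record or chance discovery at any time in the study. It makes sensor reactions reportable when they need a provider's treatment or a prescription. It then requires: "All AEs and SAEs must be resolved or deemed stable by a delegated medical doctor or equivalent before a participant completes or withdraws".

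**Section 20, Adverse Event.** The definition covers an unfavorable sign, "symptom or disease temporally associated with the intervention, regardless of whether it is considered related to the intervention".

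**Timing of the intervention.** Section 11 runs it from Day 0 to about Day 50. Section 15, Phase 2: Follow-Up Period, states: "There is no intervention during Phase 2".

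**The concern.** Section 8 gives cutaneous reactions as the known complications of CGM wear and quotes a weekly rate for them. The last sensor goes on at Contact 6, after or alongside the only AE assessment listed for Phase 2, and the one contact that follows does not ask about it. For that wear the protocol moves from asking to waiting to be told. A reaction that is still present at exit could go unrecorded. The delegated doctor's resolved-or-stable confirmation would then cover only events that someone happened to raise.

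The definition adds a second, smaller problem. Blinded sensors are worn before Day 0 and again from about Day 170, both outside the period the protocol calls the intervention. Staff deciding whether a reaction in either period is an AE get no clear answer from section 20. Because section 20 defines an SAE as an adverse event meeting certain criteria, the same uncertainty carries over to SAEs.

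What is at stake is the completeness of the safety record for one sensor wear per participant. The TIR and HEI analyses and the comparison of arms do not depend on it.

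**Working it through.** No figure in the plan is in dispute. The main check sets the passages side by side; the arithmetic only gives scale.

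**1. Does any enquiry follow the final wear?**
- The Contact 6 assessment takes place at the visit where the sensor is applied, and its described enquiry looks back 4 months. It cannot cover the 10 days ahead.
- The section 21 promise to ask applies to study visits. Contact 7 is a reminder with visit type N/A, and the receiver may be posted back, so the promise does not clearly reach it.
- Contact 7 is the last contact.

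Followed as written, the plan has no scheduled enquiry after the final wear. This rests on the contact list itself. Blank cells in the AE row of the section 4 table are not used, because the row may have lost a spanning bar when the PDF was read (the adjacent row for continuous real-time CGM use is also empty).

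**2. Does the AE definition cover that wear?**
- Against: the definition refers to the intervention (section 20), which stops at about Day 50 (section 11), and Phase 2 has none (section 15).
- For: an AE assessment is scheduled at about Day 170 (section 15), capture runs throughout the study, and treated sensor reactions are reportable with no time limit (section 21).

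The intent to collect in Phase 2 is plain, but the definition does not state it. The baseline blinded wear, before Day 0, is left equally unclear.

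**3. Scale.**

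Inputs:
- Cutaneous event rate: 0.13 to 0.15 per week of wear, 79% mild (section 8, Known Potential Risks).
- Participants expected to have follow-up CGM data: 54 per arm (section 23, Sample Size Determination). Check: 90% of 60 = 54, as stated; 2 × 54 = 108.
- Wear: up to 10 days, with 7 days as the desired minimum (section 15, Contact 6).

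Formula: expected events = participants × (days / 7) × weekly rate. More than mild = events × (1 − 0.79) = events × 0.21.

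| Wear | Rate per week | Expected events | More than mild |
|---|---|---|---|
| 10 days | 0.13 | 108 × 10/7 × 0.13 = 20.1 | 4.2 |
| 10 days | 0.15 | 108 × 10/7 × 0.15 = 23.1 | 4.9 |
| 7 days | 0.13 | 108 × 7/7 × 0.13 = 14.0 | 2.9 |
| 7 days | 0.15 | 108 × 7/7 × 0.15 = 16.2 | 3.4 |

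These are cutaneous events of any severity. The documents do not say what share needs a provider's treatment or a prescription, so the number of reportable events cannot be derived.

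**The case against.** The strongest reply is that capture does not stop at Contact 6. For this same sensor, participants are told to contact the team about any sensor concern (section 15, Phase 2: Follow-Up Period). Section 21 keeps participant report, the electronic record and chance findings open throughout. A reaction that needed a provider or a prescription is the kind of event a medical record may show. This stands. A reader might infer that reactions to the last sensor can never come to light, or that a phone call from the participant is the sole route; the documents support neither. What is missing is the systematic question.

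A reader might also infer that the definition shuts out the baseline and follow-up wear. It gives no closing date, and the scheduled Day 170 assessment and the untimed list of reportable events point the other way. Ambiguity is as far as the text goes.

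The resolved-or-stable rule can fairly be read as governing known events only, so there is no outright contradiction. The rule is still weaker when no one asks whether an event exists.

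Section 25 mentions staff checklists for each contact and section 24 a study manual. Neither is available here, and either might already contain the question. If so, the protocol only needs to say so.

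Finally, the device is commercially available, section 8 describes the added risk as minimal, and the trial has no formal safety endpoints (section 23). Only reportable AEs and SAEs enter the log, so most of the events counted above would not be reported even if asked about. This limits the weight of the point without removing it.

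**Conclusion.** The point holds as a narrow gap in safety ascertainment. No scheduled AE enquiry follows the final blinded wear, and the AE definition should say whether it covers device wear outside the intervention period.

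The unasked window would contain about 20 to 23 cutaneous events of any severity for a full 10-day wear, or 14 to 16 for 7 days, with about 3 to 5 more than mild. This assumes that the rate quoted in section 8 applies to this wear and that 108 participants wear the sensor. It is not a count of reportable events, and it should not be read as a count of events that would be lost, since some would reach the team by the other routes.

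The conclusion does not depend on whether AE questions are asked at Contacts 1 to 5, and it has no bearing on either phase's primary endpoint. It is a cheap improvement worth making.

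**What to change.** 1. Add one item to the existing Contact 7 reminder, for example in REDCap, asking about adverse events and the sensor site since Contact 6. List it under Contact 7 in sections 4 and 15. A positive answer then gives the delegated doctor something to review against the resolved-or-stable requirement.
2. Reword the section 20 definition so that it covers events associated with study devices and procedures as well as the intervention, from the first study procedure through Contact 7. Section 20 already refers to research procedures in its definition of unanticipated problems, so the wording has a precedent in the protocol.

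The cost is a protocol wording change, one survey item on a contact that already takes place, and a few more AE entries to review.

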Currently, CGM is only accessible to a limited number of people with T2D who do not use insulin but, there are some signs suggesting that expanded recommendations for CGM use and coverage may be coming.^{20,37,38} When (if) that time comes, the diabetes care community would benefit from being prepared with researched approaches for initiating the technology, especially in a way that may promote improved diet quality.

This research will also fill a knowledge gap by providing insight into the dietary intake and eating patterns of people with T2D. Results of this research may allow future interventions in people with T2D to target nutrition areas where there is the greatest room for improvement and/or impact.

The objective of the Phase 1 research is to evaluate the effect of using a NFA versus a SDA during CGM initiation on CGM-derived metrics, dietary intake, and patient-reported outcomes (PROs) in people with T2D who do not use insulin. The objective of the Phase 2 research is to help explain any impact of discontinuing CGM use in people with T2D who do not use insulin.

8. Risk and Benefit

Known Potential Risks

CGM use: CGM use is a routine part of the care for many PWD. CGM users usually report less pain or discomfort with CGM than with capillary blood glucose testing. Mild pain on insertion of CGM may be experienced by subjects at low frequency. Known allergies to medical grade adhesives is an exclusion from participation. Cutaneous complications of CGM use are typically wear-related erythema, itching, and induration. The incidence of these complications is expected to be low, 0.13 to 0.15 events per week of wear-time, with the majority (79%) being mild.³⁹ Study discontinuation rate due to skin reactions is expected to be very low.

Blood samples: Blood sample for HbA1c is a standard care procedure which could occur regardless of participation in this study; however, the interval between the baseline HbA1c and the post-intervention HbA1c is shorter than what may be recommended by routine care (approximately 60 days rather than 90 days).

Blood samples for HbA1c may be collected by venipuncture or fingerstick. Venous blood draws may cause discomfort and bruising at the puncture site. Participants may also experience lightheadedness or fainting during

CGM Initiation in People with T2D

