Potentially eligible participants will have the option to complete online self-screeners (e.g. a brief questionnaire in REDCap) or undergo brief telephone screening. Any participants who meet initial screening criteria will be further screened by study staff for eligibility. Those who are eligible and express interest in study participation will receive additional study-related information, including a copy of the informed consent form (ICF). The ICF and other study-related materials may be shared by mail or electronically (e.g. email, EMR message, etc).

Up to 300 participants may be consented in order to obtain 120 participants who provide at least seven days of baseline and post-intervention CGM assessment data. It is assumed that some participants will consent, but they will not be eligible for participation based on the required HbA1c inclusion criteria; some participants will consent but may be withdrawn (e.g. due to inadequate days of CGM data at baseline); and that there may be approximately 10% attrition during the intervention period.

CGM Initiation in People with T2D

Consenting

All participants must meet all eligibility criteria and sign the IRB-approved ICF to participate in the study. During the consent process, study staff will explain the research to the participant and the participant will have ample opportunity to review the ICF and ask questions before deciding whether or not to participate in the study. The participant must sign the ICF before any study procedures are initiated.

Of note, during the screening and consenting process, Phase 1 of the study will be described to potential participants as a study evaluating the effect of two different approaches used for introducing and initiating CGM. Details of the NFA and the SDA will *not* be described to participants in order to reduce the potential for influence if details of both study arms are described to all participants before randomization assignments are given. Phase 2 of the study will be described as an opportunity to understand what happens when someone who has used CGM stops using it.

Once the ICF is signed, a copy of the ICF will be given to the participant and a participant ID number will be assigned.

Screen Failure

Participants who sign the consent to participate and who do not meet inclusion criteria in the baseline assessment period (e.g. HbA1c or tolerance to CGM) will be considered a screen failure.

CGM Device Use

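### Section 21 leaves most expected skin reactions, and untreated reactions that end CGM wear, out of the adverse event log and the end-of-study report

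*Combined protocol and SAP*

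**What the plan says.** Section 21 (Safety Reporting) has all AEs and SAEs documented in the participant's electronic medical record. It then narrows what is carried forward: "however, only reportable AEs and SAEs will be described in end-of-study reporting". The log has the same filter: "Only reportable AEs and all SAEs will be recorded within an adverse event log". Three kinds of event are listed as reportable: severe hypoglycemia, severe hyperglycemia with DKA or HHS, and "Sensor-related reactions or infections requiring treatment by a medical provider and/or prescription medication".

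Section 8 (Known Potential Risks) names redness, itching and induration as the typical skin complications of CGM and gives their expected frequency as "0.13 to 0.15 events per week of wear-time, with the majority (79%) being mild". The next sentence predicts that very few participants will discontinue for this reason. Section 20 defines a mild event as one needing little or no treatment and not interfering with daily activities.

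Section 23 (Safety Analysis) states that there are no formal safety endpoints and refers back to the safety sections. Section 17 has participants who leave early asked for their reason, but does not say that the reasons will be summarised.

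**The concern.** The threshold depends on treatment, while the device harm that the protocol itself describes is mostly of a kind that needs little or none. Two gaps follow.

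First, most expected skin reactions would be in individual charts but in neither the log nor the final report. Second, no reportable category covers an event because of what it led to. A participant who takes the sensor off for good because of itching, without seeing a provider, has had no reportable event.

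The second gap matters more. Section 23 (Populations for Analysis) restricts the Phase 1 CGM analysis to participants with at least seven days of data at both baseline and post-intervention. Someone who stops wear early because of the skin can fall out of that set. The plan allows for 132 − 120 = 12 such losses from all causes and commits to nothing that would show how many were due to intolerance. For a trial that Section 7 presents as preparation for wider CGM use in people not on insulin, tolerability is something readers will ask about.

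**Working it through.** The plan states no figure for this point, so there is nothing to reproduce. The check has two parts: what the rules let through, and the scale.

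**What the rules let through**

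| Event | Medical record | AE log | End-of-study report |
|---|---|---|---|
| Any SAE | yes | yes | yes |
| Severe hypoglycemia; DKA/HHS | yes | yes | yes |
| Non-serious sensor reaction, treated by a provider or by prescription | yes | yes | yes |
| Non-serious sensor reaction, otherwise | yes | no | no |
| The same, but leading to sensor removal, stopping CGM or withdrawal | yes | no | no |

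**Share of skin reactions reported**

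Let *m* be the share of mild reactions, and *t* the share of non-mild reactions, that meet the treatment threshold. The documents give neither.

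- Reported share = 0.79*m* + 0.21*t*.
- With *m* = 0 and *t* between 0 and 1, the reported share lies between 0% and 21%.
- For half or more to be reported even with *t* = 1, *m* would have to be at least (0.50 − 0.21) / 0.79 = 0.37. More than a third of reactions classed as needing little or no treatment would have to be treated by a provider or by prescription. That is hard to square with the definition of mild.

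**Illustrative counts**

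Inputs: 132 enrolled and 54 per arm (108) expected in Phase 2 (Section 23, Sample Size Determination); about 10 days of baseline wear and 50 of intervention wear (Sections 11 and 15); about 10 days of follow-up wear (Section 12); 0.13 to 0.15 events per wear-week and 79% mild (Section 8). Assumptions: full wear, and that the cited rate transfers to this device and this way of collecting events.

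- Phase 1 wear: 132 × 60 / 7 = 1,131 weeks. Events: × 0.13 = 147; × 0.15 = 170. Per participant: 60 / 7 × 0.13 to 0.15 = 1.1 to 1.3.
- Phase 2 wear: 108 × 10 / 7 = 154 weeks. Events: 20 to 23.
- Total: 167 to 193 events. Mild, × 0.79: 132 to 152. Non-mild, × 0.21: 35 to 41.

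Less wear lowers the counts in proportion. The 79% share does not depend on wear.

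**The case against.** The best defence is that this is an openly stated and proportionate choice. The device is commercially available and used according to its instructions, both arms wear it, and the randomised contrast is the instruction given. Skin reactions are disclosed as a known risk. Every AE is documented in the medical record, and Section 21 requires each to be resolved or judged stable before a participant completes or withdraws. No passages conflict. That stands: this is a gap in what will be described, not an error and not a failure to record events.

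Several stronger readings are tempting but not supported.

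- *That end-of-study safety reporting covers treated sensor reactions only.* It also covers all SAEs, severe hypoglycemia and DKA/HHS.
- *That the trial would publish a near-zero reaction rate.* On the illustrative figures 35 to 41 reactions are not mild, and the treated share is unknown. A mild reaction can also occasionally be treated. The report would give treated reactions, not all reactions.
- *That the arms would differ, or the primary comparison be biased.* Device and wear instructions are the same in both arms, and the documents suggest no mechanism.
- *That baseline intolerance disappears from the enrolled population.* Section 15 (Screen Failure) does give "e.g. HbA1c or tolerance to CGM) will be considered a screen failure", but the Baseline Period text counts anyone meeting the HbA1c criterion as enrolled and defines screen failure there by HbA1c alone. How such participants are classified is unclear.

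The list of reportable events is introduced by a word that could be read as open-ended, but no further category is given and the sensor item carries its own threshold. Days of wear and percent sensor activity are planned outcomes, but they are CGM metrics, so the seven-day analysis set applies to them and they do not show why someone stopped.

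A rate per wear-week would also promise too much. Events come from participant report, record notification or incidental finding. The detailed schedule lists an adverse event assessment only at Contact 6, when the follow-up sensor is applied. Contact 7 is a reminder, with postal return of the receiver possible, so no visit follows that wear.

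**Conclusion.** The point holds for non-serious sensor reactions. As written, most expected skin reactions would be in neither the log nor the final report, and an untreated reaction that ended wear or participation would not be described. The conclusion that most are omitted rests on the protocol's own 79% and its definition of mild, and survives unless more than about 37% of mild reactions meet the treatment threshold. The 167 to 193 events only illustrate scale under full wear and a transferable rate.

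The consequence is limited. The report could not confirm that discontinuation for skin reactions was as rare as Section 8 predicts, nor say how many losses from the seven-day CGM set were due to intolerance. If the prediction is right, such losses will be few. Sample size, power and the primary test do not depend on this. It is a cheap improvement to consider, not a correction that the trial needs before it can proceed.

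**What to change.** Keep the present definition of a reportable AE for IRB reporting. Amend the end-of-study sentence in Section 21 so that the report also describes:

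1. Any AE that led to sensor removal, CGM discontinuation or study withdrawal, by period (baseline, intervention, follow-up) and by arm after Day 0. Include participants who exit for CGM intolerance during baseline wear, whatever label they are given.
2. A simple count, by severity, of participants with a sensor-site reaction documented in the medical record. Label it as passively collected and likely an undercount, particularly for the follow-up wear.

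Full log entries for every mild event, with all the fields that Section 21 requires, are not needed, and a rate per wear-week should not be attempted with this form of collection.

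The cost is one wording change, some abstraction from medical records and from the withdrawal reasons already requested under Section 17, and one descriptive table. Visits, procedures, clinical care and IRB reporting stay as they are.
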